6.8. Appendix 8: Definition of Diabetic Status

For the purposes of the subgroup analysis on diabetic status, participants will be defined as diabetic if, prior to being randomly assigned, they possess ANY of

- baseline hemoglobin A1c levels greater than 6.5%
- concomitant medications classified as a *drug used in diabetes* according to the Anatomical Therapeutic Chemical (ATC) level 2 code A10.
- medical history classified under the MedDRA PT Diabetes Mellitus, or
- medical history classified under the MedDRA LLT *Diabetes Mellitus*.

7. References

Signature Page for VV-CLIN-072145 v1.0 $\,$

Approval	PPD
	02-Jun-2023 11:44:12 GMT+0000

Signature Page for VV-CLIN-072145 v1.0

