Inclusion and exclusion criteria, review and confirm	X	X													Confirm inclusion and exclusion criteria prior to randomization and administration of first dose of study intervention.
Demographics	X														Includes ethnicity (where permissible), year of birth, sex, and race.
Preexisting conditions and medical history	X														Collect all ongoing conditions and relevant past surgical and medical history including history of premature CV disease.
Prespecified medical history (indication and history of interest)	X														Additional data for the indication and comorbidities of interest.
Substance use (alcohol)	X	X	X	X	X	X	X	X	X	X	X	X	X	X	
Concomitant medications	X	X	X	X	X	X	X	X	X	X	X	X	X	X	

Study J3F-MC- EZCB(e)	Screening	Double-Blind Treatment and Assessment											Follow-up	Comments	
		1	2	3	4	5	6	7	8	9	10	11			12
Remote Visits			X	X	X		X	X		X	X				V801 on-site for all sites including the US
Visits	1	2	3	4	5	6	7	8	9	10	11	12	ED	801	ED = early discontinuation.
Days from randomization	-45	0	15	30	60	90	120	150	180	210	240	270	—	360	
Visit interval tolerance (days)		—	±3	±3	±3	-5 to +10	±7	±7	±7	±7	±7	±7	—	±7	Visit 1 procedures may be conducted over more than 1 day if all activities are completed within the allowable visit tolerance.
Fasting Visit	X	X	X	X	X	X	X	X	X	X	X	X	X	X	Participants should not eat or drink anything but water for 8 hours before the visit. If a participant arrives not fasted, schedule the laboratory draw for another date.
Adverse events (AEs)	X	X	X	X	X	X	X	X	X	X	X	X	X	X	Any events that occur after signing the informed consent are considered AEs as defined in Section 10.3. If an injection-site reaction occurs, collect an additional unscheduled immunogenicity and PK sample (Section 8.3.4).
Physical Evaluations															
Height	X														Participant should remove shoes.
Weight	X					X			X			X	X	X	
Vital signs	X	X	X	X	X	X	X	X	X	X	X	X	X	X	Includes blood pressure and pulse rate. May repeat measure once. Measure after participant has been sitting at least 5 minutes and before ECG tracing and collection of blood samples for laboratory testing.
Physical examination	X											X	X		See Section 8.2.1. The complete physical examination excludes pelvic, rectal, and breast examinations, unless clinically indicated.

Study J3F-MC- EZCB(e)	Screen ing	Double-Blind Treatment and Assessment											Follow- up	Comments	
				X	X	X		X	X		X	X			
Remote Visits			X	X	X		X	X		X	X				V801 on-site for all sites including the US

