5.2. Exclusion Criteria

Participants are excluded from the study if any of the following criteria apply:

Diabetes and cardiovascular medical conditions

12. Have, in the 6 months prior to screening, uncontrolled Type 1 or Type 2 diabetes, defined as an episode of ketoacidosis or hyperosmolar state requiring hospitalization, or have an HbA1c $\geq 8\%$ at screening.
13. Have a history of nephrotic syndrome.
14. Have had within the past 3 months prior to screening
 - a. Myocardial infarction
 - b. Unstable angina
 - c. Coronary artery bypass graft
 - d. Percutaneous coronary intervention – diagnostic angiograms are permitted
 - e. Peripheral artery disease
 - f. Transient ischemic attack, or
 - g. Cerebrovascular accident.
15. Have New York Heart Association Class III or IV heart failure or last known left ventricular ejection fraction $< 30\%$.
16. Have undergone LDL apheresis within 12 months prior to screening.

Other medical conditions

17. Have a TSH outside of the 0.4 to 6.0 mIU/L range.
18. Have a history or presence of an underlying disease, or surgical, physical, or medical condition that, in the opinion of the investigator would potentially affect participant safety within the study or interfere with the interpretation of data.
19. Have, within 1 year prior to screening or plan on having during the study, surgical treatment for obesity.
20. Have within 5 years prior to screening a history of an active or untreated malignancy or are in remission from a clinically significant malignancy.

Exceptions:

- Basal or squamous cell skin cancer.
 - Cervical carcinoma in situ or prostate cancer in situ.
21. Have a history of or current significant psychiatric disorders considered clinically significant in the opinion of the investigator.
 22. Have within 3 years prior to screening a history of chronic alcohol abuse, IV drug abuse, or other illicit drug abuse.
 23. Have within 3 months prior to screening used marijuana or tetrahydrocannabinol containing products or are unwilling to abstain from use during the study.
 24. Have 2 or more clinically significant or severe drug allergies, or severe post-treatment hypersensitivity reactions, including, but not limited to
 - a. erythema multiforme major
 - b. linear immunoglobulin A dermatosis
 - c. toxic epidermal necrolysis, or

- d. exfoliative dermatitis.
- 25. Have a history of acute or chronic pancreatitis.

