6.8. Concomitant Therapy

See Section 10.7 for lists of medications that are permitted or prohibited in this study.

Concomitant therapy regimens

All participants should maintain their usual medication regimens for concomitant conditions or diseases throughout the study, unless those medications are specifically excluded in the protocol.

Participants taking concomitant medications should be on stable dosages at the time of screening and should remain at stable dosages throughout the study, unless changes need to be made because of AEs.

Changing concomitant therapy

Participants should consult with authorized study personnel before taking any new medications or supplements during the study. Authorized study personnel should consult the sponsor's medical monitor if there are any questions about concomitant therapies during the study.

The investigator or the participant's usual diabetes care physician is responsible for changes in diabetic medications.

Concomitant therapy data collection

For therapy that the participant is receiving at the time of enrollment or receives during the study, authorized study personnel should collect

- the name of medication, vaccine or therapy
- the reason for use, and
- dates of administration, including start and end dates.

For diabetes and lipid modifying medications, such as statins and PCSK9 inhibitors, collect dosage information including dose and frequency.

7. Discontinuation of Study Intervention and Participant Discontinuation/Withdrawal

Discontinuation of specific sites or of the study as a whole are handled as part of Section 10.1.9.

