4.6.2. Adverse Events

A TEAE is defined as an event that first occurred or worsened in severity after first dose. The Medical Dictionary for Regulatory Activities (MedDRA) Lowest Level Term (LLT) will be used in the treatment-emergent derivation. The maximum severity for each LLT during the baseline period, including ongoing medical history, will be used as baseline severity. Events with a missing baseline severity will be treated as "mild" in severity for determining treatment-emergence. Events with a missing severity during the postbaseline period will be treated as "severe" and treatment-emergence will be determined by comparing to baseline severity.

For events occurring on the day of first taking study medication, the case report form collected information (for example, treatment emergent flag, start time of study treatment, and event) will be used to determine whether the event was pre- versus post-treatment if available. If the relevant information is not available, then the events will be counted as posttreatment.

The counts and percentages of participants with TEAEs will be summarized by treatment using MedDRA Preferred Term (PT) nested within the System Organ Class (SOC). Statistical comparisons will be applied at both the SOC and PT levels. Events will be ordered by decreasing frequency within SOC. The SOC will be in alphabetical order. For events that are sex-specific, the denominator and computation of the percentage will include only participants from the given sex

An overview of the number and percentage of participants who experienced a TEAE, serious adverse event (AE), death, discontinued from study treatment or study due to an AE, and TEAE relationship to study drug will be summarized by treatment.

The counts and percentages of patients with TEAEs by maximum severity will be summarized by treatment using MedDRA PT. For each participant and TEAE, the maximum severity for the MedDRA PT is the maximum postbaseline severity observed from all associated LLTs mapping to the MedDRA PT. The maximum severity will be determined based on the non-missing severities. If all severities are missing for the defined postbaseline period of interest, it will show as missing in the table.

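### The diabetic-status rule names only the untyped history term and takes any A10 drug whatever its use, so it can mislabel some participants and weaken the diabetic-subgroup interaction

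*SAP*

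**What the plan says.** SAP Section 6.8 (Appendix 8) defines a participant as diabetic if, "prior to being randomly assigned, they possess ANY of" four things:

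- "baseline hemoglobin A1c levels greater than 6.5" per cent;
- a concomitant medication classed as a diabetes drug "according to the Anatomical Therapeutic Chemical (ATC) level 2 code A10";
- "medical history classified under the MedDRA PT Diabetes Mellitus";
- medical history under the MedDRA LLT of the same name.

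The label is used in SAP Section 4.7, where diabetic versus non-diabetic is one of several subgroup analyses of the primary endpoint. Each is run as an MMRM within the subgroup and as an MMRM with interactions. SAP Section 4.1 tests interactions at a 2-sided alpha of 0.10.

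Protocol Section 5.2, criterion 12, excludes "uncontrolled Type 1 or Type 2 diabetes" in the 6 months before screening, or HbA1c of 8% or more at screening. Controlled diabetes of either type is therefore admitted. Criterion 42 allows medication associated with weight change if the dose has been stable for at least 3 months and will stay so. For each concomitant therapy, Protocol Section 6.8 collects "the reason for use". The Schedule of Activities adds a prespecified medical history at screening: "Additional data for the indication and comorbidities of interest".

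**The concern.** The rule is closed: it lists what counts and leaves nothing to judgement. Followed literally, it leaves room for error in both directions.

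**Missed diabetics.** The history routes name the untyped term only. The SAP does not say how an entry of type 1 or type 2 diabetes is matched. If such an entry is coded under another term, it satisfies neither history route.

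**Non-diabetics labelled diabetic.** One A10 drug is enough, whatever it was taken for. Stable weight-related medication is allowed in the trial, and the rule does not use the field that records why a drug is taken.

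The subgroup analysis is there to check whether the effect is consistent. Errors in a baseline label that are unrelated to treatment and to response mix the two groups and bring their estimated effects closer together. At stake is the sensitivity of that one check.

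**Working it through.** **The plan's own figure.** Protocol Section 9.5 randomizes 175 in a 2:1:2:2 ratio, i.e. 50:25:50:50. With 20% dropout this leaves 40:20:40:40 completers, as stated. For a difference of 30 points and SD 15:

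- 100 mg versus placebo: SE = 15 × √(1/20 + 1/40) = 4.11, ratio 30/4.11 = 7.30.
- 400 or 800 mg versus placebo: SE = 15 × √(1/40 + 1/40) = 3.35, ratio 30/3.35 = 8.94.

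Power exceeds 99% in both cases, so the stated figure reproduces. The documents give no power for any interaction and no figure for the diabetic subgroup.

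**Who can be mislabelled.** One route is enough, so a diabetic is missed only if all three conditions hold: HbA1c at or below 6.5%, no A10 drug, and history coded under another term. A non-diabetic is wrongly included if an A10 drug is recorded for another purpose. The documents do not show that either kind of participant is in the trial.

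**Effect on the interaction.** The label is fixed before randomization, so errors cannot depend on the arm. Assume also that a mislabelled participant responds like others of the same true status. Then

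observed interaction = true interaction × (PPV + NPV − 1).

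With prevalence p, sensitivity Se and specificity Sp, the share labelled diabetic is q = p·Se + (1 − p)(1 − Sp). PPV = p·Se/q and NPV = (1 − p)·Sp/(1 − q).

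*Example (assumed): p = 0.35, Se = Sp = 0.95.*

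- q = 0.3325 + 0.0325 = 0.365
- PPV = 0.3325/0.365 = 0.911
- NPV = 0.6175/0.635 = 0.972
- Share of the interaction retained = 0.911 + 0.972 − 1 = 0.88
- Missed: 175 × 0.35 × 0.05 ≈ 3. Wrongly included: 175 × 0.65 × 0.05 ≈ 6.

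Share retained under other assumptions:

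| Prevalence | Se | Sp | Retained |
|---|---|---|---|
| 0.20 | 0.90 | 0.90 | 0.67 |
| 0.20 | 0.95 | 0.95 | 0.81 |
| 0.35 | 0.90 | 0.90 | 0.77 |
| 0.35 | 0.95 | 0.95 | 0.88 |
| 0.50 | 0.90 | 0.90 | 0.80 |
| 0.50 | 0.95 | 0.95 | 0.90 |
| any | 1.00 | 1.00 | 1.00 |

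At 20% prevalence, wrong inclusions do most of the harm: specificity of 0.95 alone gives 0.83, and sensitivity of 0.95 alone gives 0.99.

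**Effect on power.** Use a 2-sided normal test at alpha 0.10, SD 15, an assumed true interaction of 10 points, and SE = 15 × √[(1/n₁ + 1/n₂)(1/q + 1/(1 − q))]. This is a single-visit approximation on the percent-change scale, not the SAP's MMRM on the log scale.

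- 40 versus 40, p = 0.35, perfect label: SE = 7.03, power 41%.
- Same, Se = Sp = 0.95: effect 8.83, SE = 6.97, power 36%.
- 40 versus 40, prevalence 20–50%: power 33–44% with a perfect label and 27–38% at 0.95/0.95.
- 20 versus 40 (100 mg), perfect label, same prevalence range: power 0.255–0.337.

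**The case against.** The strongest objection is that both directions of error rest on facts the documents do not give. They do not show that typed diabetes is coded away from the named PT. They do not show that any participant takes an A10 drug for a purpose other than diabetes; Appendix 8 itself describes A10 as drugs used in diabetes, and criterion 42 does not name that class. The prevalence and error rates are assumptions too. All of this stands, so the finding is that the rule can mislabel participants, not that it does. What remains is the text itself: the typed forms are not listed, and the drug route ignores a field that is collected.

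Several stronger readings are tempting but not supported:

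- *A reader might infer that the whole rule depends on one exact term.* It does not. History is one part of an ANY rule that also has HbA1c and drug routes, and a PT match takes in every LLT under that PT.
- *A reader might infer that the LLT line adds nobody.* SAP Section 4.6.2 shows the hierarchy in general, with severity "observed from all associated LLTs mapping to the MedDRA PT". It does not show where this LLT sits.
- *A reader might infer that a participant with HbA1c of exactly 6.5% is wrongly placed.* Nothing in the documents contradicts the cut-off, and such a participant can still qualify by drug or history.
- *A reader might infer that a finding of consistency is made too easy.* SAP Section 4.7 sets no decision rule for consistency.

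It is also fair to say that sample size limits this analysis more than the label does: power for a 10-point interaction is below one half even with a perfect label.

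**Conclusion.** The point holds as a minor one. Followed as written, the rule can miss a narrow group of diabetics and can include non-diabetic users of A10 drugs, and either error would weaken the diabetic-subgroup interaction. With assumed prevalence of 20–50% and sensitivity and specificity of 0.90–1.00, between 67% and 100% of the interaction is retained (81–100% if both are at least 0.95). The upper end is no loss at all, and the documents cannot say where in the range the trial lies. The formula also needs mislabelled participants to respond like others of their true status; if they do not, the loss could be smaller or larger. One subgroup analysis is affected. The primary comparison is not, because diabetic status is not a term in its model.

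**What to change.** Amend SAP Appendix 8 before unblinding:

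1. Replace the two history lines with a listed set of diabetes terms that explicitly includes type 1 and type 2. SAP Appendix 6 already uses multi-term searches for other concepts.
2. Count an A10 drug only when its recorded reason for use is diabetes.
3. Confirm the resulting labels in one blinded listing of HbA1c, A10 drugs with reason for use, and coded history.

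Leave the HbA1c cut-off as written. The cost is a few lines of SAP text and one listing review, with no new data. If the listing shows that nobody changes group, the amendment has done no harm.
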